4.4 Subgroup analysis

To determine whether the treatment effect is consistent across various subgroups the betweengroup treatment effect for the primary and secondary efficacy endpoints will be estimated within each category of the following pre-specified variables.

Main subgroup analyses:

- Number of radiotherapy fractions per day (once or twice per day)
- Tumour stage (I/II/III by 7th TNM classification)
- Gender

Other pre-planned subgroup analyses:

- Age group
- ECOG performance status (at randomization)
- Smoking history
- Status according to biological markers (if available)

Notes:

- 1. In case of imbalance in number of patients with the subgroups created by treatment and the variables of interest, this subgroup analysis will not count in the multiple comparison adjustment.
- 2. These analyses are also described above in the description of PFS, OS analyses.

4.5 Sensitivity analysis

In a sensitivity analysis framework, PFS, OS and TTF (efficacy cohort) will be evaluated having as start date the date of enrolment. In case of patients enrolled after their first chemotherapy cycle, further adjustment will be made to the start date (start date will be the date of 2^{nd} chemotherapy cycle minus 21 days).

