- 1 ≤ 28 days prior enrolment; if the first chemotherapy cycle has been administered before enrolment, baseline evaluations must have been done within 35 days before start of first chemotherapy cycle.
- 2 **Chemotherapy** consists of platinum compound (cis- or carboplatin) and etoposide combination and is given for 4 cycles (1 cycle = 21 days). Chemotherapy should start within 7 days after enrolment. If the start of chemotherapy cannot be delayed, a maximum of 1 chemotherapy cycle can be administered before enrolment.
- 3 **Randomisation** should take place 5 - 6 weeks from day 1 of chemotherapy cycle 4 (between days 35 and 42 of cycle 4). All examinations have to be done within 7 days prior randomisation (except for tumour assessment, which has to be done within 14 days before randomisation).
- 4 **Consolidation treatment** should start 6-8 weeks (42-56 day) from start of chemotherapy cycle 4, and not more than 2 weeks (14 days) after the date of randomisation.
- 5 **Induction phase:** nivolumab (1 mg/kg i.v. over a period of 30 minutes) followed (on the same day) by ipilimumab (3 mg/kg i.v. over a period of 90 minutes), once every 3 weeks (+/- 3 days, without dosing delay), for 4 cycles.
- 6 **Maintenance phase:** nivolumab (240 mg i.v. over a period of 30 minutes), once every 2 weeks (+/- 2 days, without dosing delay) until PD, for a maximum of 1 year from start of maintenance phase. The first dose of maintenance nivolumab will be administered 3 weeks after the last IMP doses of induction phase.

- 7 **Observation arm:** patients should be documented 9 and 18 weeks (+/- 3 days) after randomisation and thereafter every 18 weeks (+/- 1 week), according to local standard of follow-up, until PD or for maximum 15 months after randomisation. The following laboratory values are to be measured: haematology, renal function, hepatic function, Na and K. Beyond 15 months after randomisation or upon PD patients will enter the follow-up phase.  
CT scans for tumour assessment are done at the same schedule as for patient in the experimental arm (see footnote 13).
- 8 **Follow-up:**  

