## **10. Trial treatments**

### **10.1. Overview of treatment sequence**

10.1.1. **After enrolment**, the patient will receive or, if included after the first chemotherapy cycle, continue receiving standard of care treatment for limited disease SCLC consisting of chemo-radiotherapy and PCI

- **Chemotherapy:** will be started in the week following enrolment (alternatively, maximum 1 cycle of chemotherapy may be administered before enrolment), and consists of a total of 4 cycles of cisplatin (25 mg/m^2 i.v. on days 1 – 3 or 75 mg/m^2 on day 1) or carboplatin (AUC 5-6, calculated according Calvert formula, i.v. on day 1), plus etoposide (100 mg/ m^2 i.v. days 1 – 3), repeated every 3 weeks (+/- 3 days without cycle delay).
- **Concomitant Thoracic Radiotherapy:** Accelerated twice-daily administration of 45 Gy in 30 twice-daily fractions of 1.5 Gy (6-8 hours apart), 5 days per week for 3 weeks, or an allowed, but not-recommended schedule of 56 Gy, given in

28 once-daily fractions of 2 Gy, 5 days per week for 6 weeks. Two options are allowed: Thoracic radiotherapy MUST start either from day 1 of cycle 1 or day 1 of cycle 2.

Radiotherapy start at day 1 of cycle 3 is allowed if patient is enrolled after the first cycle only but should be exceptional. Optimally, radiotherapy should start at the latest on day 1 of cycle 2.

- **Prophylactic Cranial Irradiation (PCI):** 25 Gy in 10 fractions starting between day 8 and day 15 of chemotherapy cycle 4 and finished not later than day 29 from start of cycle 4.

10.1.2. **After randomisation**, which should take place within 5-6 weeks after day 1 of cycle 4 (between days 35 and 42 of cycle 4)

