**Table 6: Dose modifications of carboplatin/etoposide for haematological toxicity**

Dose modifications are based on pre-chemotherapy blood count.

ANC x 10  /L		Platelets x 10  /L	Carboplatin /Etoposide
≥ 1.5 at day 1 of cycle	and	≥100	Full dose
<1.5 at day 1 of cycle	or	<100	Delay until recovery ANC ≥ 1.5 and Platelets >100

ANC x 10  /L		Platelets x 10  /L	Carboplatin /Etoposide
Febrile neutropenia episode or treatment delay for Grade 4 neutropenia >7 days			First event: full dose and G-CSF support is recommended. Second event or if G-CSF support was already delivered: 20% dose reduction and continuing G-CSF support. Third event despite 20% dose reduction and G-CSF support: 35% dose reduction Subsequent event: off trial
		Grade 4 thrombocytopenia requiring medical intervention or $\geq$ Grade 2 bleeding with thrombocytopenia	First event: 20% dose reduction Second event: 35% dose reduction Subsequent event: off trial

If chemotherapy cannot be administered after a 3-week delay because of haematological toxicity, chemotherapy should be discontinued. If Hb<10, blood transfusions will be required.

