#### **Table 16: Case report forms**

CRF in ETOPdata	To be completed
Eligibility for Enrolment	
Within 28 days after start of baseline assessments.
 
Prior to start of 2nd cycle of chemotherapy and thoracic radiotherapy if the patient could not be enrolled before the 1st cycle of chemotherapy.

Baseline for Chemotherapy	
Within 14 days after enrolment

Tumour Assessment	
Before randomisation
 
Baseline before enrolment: within 14 days after enrolment;
 
Baseline before randomisation: between 3-6 weeks after day 1 of chemotherapy cycle 4;
 
After randomisation: within 14 days of date of CT scans, which take place as follows until tumour progression:
 
- up to 18 months: every 9 (+/- 1) weeks
 
- up to 2 years: every 12 (+/- 1) weeks
 
- years 3 and 4: every 26 (+/- 1) weeks
 
- at 5 years: week 260 (+/- 1)

Concomitant Medication	
Continuously from date of enrolment to 30 days after end of trial treatment (100 days if applied for the treatment of AEs and/or SAEs).

Chemotherapy Cycles	
Within 14 days after the last administration of chemotherapy in each cycle.
 
For patients that have been enrolled after the first chemotherapy cycle, an eCRF providing information about the 1st chemotherapy cycle has to be submitted within 14 days after enrolment.

Thoracic Radiotherapy and PCI	
Within 14 days of last day of each radiotherapy

Adverse Events Chemo-radiotherapy	
At baseline: within 14 days after enrolment (to record symptoms present at baseline);
 
Within 14 days of end of each cycle of chemo-radiotherapy;
 
Within 14 days after randomisation;
 
Within 14 days of end-of-treatment visit if patient does not proceed to randomisation.

CRF in ETOPdata	To be completed
Biological Material Tracking	
This eCRF is to be completed incrementally.
 
Entries are to be made:
 
 
- immediately after local storage of blood/serum samples (on same day).
 
- immediately after submission of material (FFPE and blood/serum) for central biobanking (on same day).
 

Baseline before Randomisation	Within 14 days after randomisation
Eligibility Check and Randomisation	After end of chemo-radiotherapy, for randomisation

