2.3 Analysis population

Efficacy cohort: The efficacy cohort is the Intention-to-treat (ITT) population of the trial and includes all randomized subjects under protocol AM1. Patients will be evaluated in the treatment arms to which they were randomly assigned, regardless of the treatment actually received, including patients who were randomized but did not receive any trial treatment.

Safety cohort: The safety cohort consists of all subjects who have received at least one dose of IMP treatment plus all patients randomized to observation arm (under protocol AM1).

Patients will be evaluated according to the treatment they actually received, irrespective of their allocated treatment at randomization.

Per-Protocol cohort: Per-protocol cohort includes all patients enrolled under protocol AM1.

Per-Protocol safety cohort: Per-protocol safety cohort includes all patients enrolled under protocol AM1, who received at least one dose of chemo-radiotherapy after enrollment.

3 Primary efficacy analysis of PFS

Primary efficacy analysis of PFS (primary endpoint) will be performed on **all randomized patients under AM1 protocol, based on their initial treatment assignment (ITT, efficacy cohort)**. PFS time is measured from time of randomization.

Formal hypothesis testing

Based on the protocol AM1 and after the modifications arose from the premature study accrual termination, the trial is designed to test the hypotheses that treatment with chemoradiotherapy and PCI followed by consolidation treatment (nivolumab plus ipilimumab) will lead to an increase in median PFS to 22.8 months, from 13.1 months under treatment with chemoradiotherapy and PCI without consolidation treatment. According to the study design, this corresponds to a PFS HR of 0.57. Using 80% power and a one-sided type I error of 5%, a total of 81 PFS events are needed to observed in order to achieve the trial goal.

In the frame of final efficacy analysis, the **formal comparison** of the PFS between the two treatment arms, will be based on **stratified log-rank test** (with number of fractions of radiotherapy [1/2] and administration of FDG-PET-CT [Yes/No] being the stratification factors). Unstratified log-rank test will be also calculated. This would be of particular value in case at least one stratum level has very low number of patients.

Further PFS analyses

The following **PFS analyses** will also be performed and presented

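### SAP 4.5 imputes the start date of late-enrolled patients from cycle 2 when the cycle 1 date should be on file, and does not label its from-enrolment estimates as conditional on randomisation

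*SAP*

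**What the plan says.** SAP 4.5 states that "PFS, OS and TTF (efficacy cohort) will be evaluated having as start date the date of enrolment". For patients enrolled after their first chemotherapy cycle, it moves the start to the date of the second "chemotherapy cycle minus 21 days". The efficacy cohort (SAP 2.3) "includes all randomized subjects under protocol AM1". SAP 4.6 adds a descriptive OS analysis from enrolment for everyone enrolled under amendment 1, randomised or not. It too adjusts the start for late-enrolled patients, but gives no formula.

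The protocol bears on this in four places:

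- Table 16 (section 17.1): for patients enrolled after cycle 1, an eCRF with information on the first "chemotherapy cycle has to be submitted within 14 days after enrolment".
- Sections 2 (footnote 1), 16.1.1 and 16.2: for the same patients, baseline evaluations must fall within the 35 days before the first cycle started.
- Sections 7.3 and 8.2: randomisation requires completed chemo-radiotherapy and PCI and no progression, and falls on days 35–42 of cycle 4.
- Section 18.4: the from-enrolment results are a secondary presentation. The main results run from randomisation.

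**The concern.** There are two separate issues.

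**Start date.** The SAP derives a date from cycle 2 although the date it approximates should be on file. The approximation is exact only if cycle 2 came exactly 21 days after cycle 1. Delay is foreseen: the text after Table 6 begins "If chemotherapy cannot be administered after a 3-week delay because of haematological toxicity" and sets discontinuation as the consequence, and Tables 7 and 8 allow up to 3 weeks for hepatic toxicity. The rule also presupposes that cycle 2 was given. That holds for every randomised patient, but not for every enrolled patient.

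**Guaranteed event-free time.** A patient who progresses or dies before randomisation is not in the efficacy cohort. Starting the clock at enrolment therefore adds a stretch in which nobody in the cohort can fail. Medians and landmark rates labelled as from enrolment could be read as what a newly enrolled patient can expect. They describe only those who reached randomisation. SAP 4.5 does not say so.

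**Working it through.** **1. Enrolment to randomisation**

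Inputs:
- Chemotherapy "is given for 4 cycles (1 cycle = 21 days") (Protocol 2, footnote 2), so cycle 4 starts 3 × 21 = 63 days after cycle 1.
- Randomisation 35–42 days after cycle 4 day 1 (Protocol 8.2).
- Chemotherapy within 7 days after enrolment (Protocol 8.1).

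From cycle 1 day 1 to randomisation: 63 + 35 = 98 to 63 + 42 = 105 days, or 14.0–15.0 weeks. This agrees with Protocol 14.3, which puts the post-chemo-radiotherapy tumour assessment at around week 15.

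From enrolment before chemotherapy: 98 to 105 + 7 = 112 days, or 3.2–3.7 months (30.44 days per month). Variations:
- Cycles are "repeated every 3 weeks (+/- 3 days without cycle delay"). Three intervals at the extremes give 98 − 9 = 89 to 112 + 9 = 121 days (2.9–4.0 months).
- With the full 6 weeks of permitted delay (Protocol 10.3), the upper end is 112 + 42 = 154 days (5.1 months).
- A patient enrolled just before cycle 2 and keeping the enrolment date would have 42 + 35 = 77 to 42 + 42 = 84 days. The adjustment brings this back to 98–105, so adjusting is sensible in itself.

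**2. Effect on absolute estimates**

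Assume exponential times from randomisation at the design medians m (13.1 and 22.8 months for PFS, 20.7 for observation-arm OS) and a shift s of 3.22–3.68 months. The median becomes m + s, and the rate at time t becomes 0.5^((t − s)/m).

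| Estimate | From randomisation | From enrolment |
|---|---|---|
| Observation-arm median PFS | 13.1 months | 16.3–16.8 months |
| Experimental-arm median PFS | 22.8 months | 26.0–26.5 months |
| Observation-arm 1-year PFS | 53% | 63–64% |
| Observation-arm 2-year OS | 45% | 50–51% |

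The ratio of PFS medians moves from 13.1/22.8 = 0.575 to about 0.63.

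**3. Effect on the treatment comparison**

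A simulation with 150 patients (assumed), a true hazard ratio of 0.575 and 1,500 runs gave a mean hazard ratio of 0.572 from randomisation and 0.572 from enrolment for shifts of 98–112 days. For shifts of 98–154 days it was 0.567 for both. One-sided rejection under no effect was 0.044–0.047 throughout.

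**4. Would delayed entry at randomisation help?**

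A second simulation used a 13.1-month exponential from randomisation, 75 patients and uniform censoring at 12–48 months (the last two assumed). The mean estimated median from enrolment was:

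| Entry (uniform) | Everyone at risk from enrolment | Delayed entry |
|---|---|---|
| Days 98–112 | 16.6 months | 16.4 months |
| Days 98–154 | 17.2 months | 16.3 months |

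Nobody is at risk before about day 98, so the delayed-entry curve stays conditional on getting that far.

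**5. Error in the imputed start**

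Let cycle 2 start 21 + d days after cycle 1. The imputed start is then cycle 1 day 1 + (21 + d) − 21, so it is wrong by exactly d days.
- Within the window, d lies between −3 and +3.
- With a 3-week delay, d = +21. The start is 21 days late and the reported time 21 days too short.
- Example: cycle 1 on day 1, enrolment on day 5, cycle 2 on day 43. The imputed start is day 43 − 21 = 22, which is 17 days after enrolment. The adjustment then moves the start the wrong way.
- With no cycle 2, the rule returns nothing. This can arise only among enrolled patients who were not randomised, that is, in SAP 4.6.

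**The case against.** The strongest reply is that nothing inferential depends on this. Primary PFS runs from randomisation, the from-enrolment results are a secondary presentation, and the extra interval precedes randomisation and so cannot depend on the arm. That stands. A reader might infer that immortal time biases the treatment comparison; step 3 shows that it does not.

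Second, a from-enrolment median in a cohort stated to be randomised patients is a valid description of that cohort. Both documents say that randomised patients have a better prognosis than all those enrolled, and SAP 4.6 already gives OS for all enrolled. This also stands, and it reduces the second issue to labelling. A reader might expect these medians to be set against published from-diagnosis figures, but neither document plans that.

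Third, a reader might infer that the SAP overwrites a recorded cycle 1 date. It does not. It replaces the enrolment date, moving the start towards true treatment start, and passes over the recorded date. Table 16 promises only information on cycle 1; that this includes the date is a close inference, supported by the 35-day window. The 3-week error is a worst case, confined to late-enrolled patients with a delayed cycle 2, whose number the documents do not give. It shortens times, the opposite direction to the guaranteed period.

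**Conclusion.** The point holds as a minor correction to secondary analyses. The 21-day rule is a needless approximation: at most 3 days out within the cycle window, up to about 3 weeks late after a delayed cycle 2, and undefined without a cycle 2. The last consequence assumes that SAP 4.6 uses the rule of 4.5, which is likely but not written.

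The from-enrolment medians and rates in the efficacy cohort carry about 98–112 event-free days on the nominal schedule. Observation-arm PFS would read about 16.3–16.8 months against 13.1, assuming exponential times at the design median. The hazard ratio, its test and the primary analysis are unaffected.

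Two remedies that a reader might reach for do not follow. Delayed entry at randomisation leaves the conditioning in place (step 4). Adding PFS for all enrolled patients would not be clean, because the protocol gives no scan schedule for those not randomised.

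**What to change.** - In SAP 4.5 and 4.6, define the adjusted start for late-enrolled patients as the recorded cycle 1 day 1 date. Keep cycle 2 less 21 days only as a fallback when that date is missing, and say what applies if neither date exists.
- In SAP 4.6, state that formula explicitly.
- In SAP 4.5, label the from-enrolment medians and rates as conditional on reaching randomisation.
- Take from-enrolment OS for the enrolled population from SAP 4.6. Note there that late-enrolled patients still carry the time between cycle 1 and enrolment as event-free: up to about 21 days, since enrolment must precede cycle 2, and longer if cycle 2 was delayed.

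The cost is a few lines of SAP text and a change to one derived variable. No new data are needed if, as inferred, the eCRF holds the cycle 1 date; confirm this first.

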4.6 Descriptive analysis of the per-protocol cohort

For all patients enrolled under protocol AM1, irrespective of whether they were subsequently randomized or not, the following will be presented:

- Objective response to chemo-radiotherapy based on the tumour assessment performed before randomization.
- All reasons for non-randomization (included in section 4.2).
- OS analysis (KM plot, median OS, 1 and 2-year rates with 95% CIs) with start date the enrolment date, further adjusted for patients enrolled after the first chemotherapy cycle.

4.7 Safety analysis

The safety analysis will be based on the safety cohort, i.e., all patients who have received at least 1 dose of IMP treatment (experimental arm) plus all patients randomized to observation arm, and will include the following:

- Overview of the number of patients who experienced an AE and/or a SAE, as well as
 the number of patients in the safety cohort who did not experience an event, along with
 respective percentages will be shown. This information will be presented overall and by
 treatment arm. Also, number of patients that entered the study with baseline symptoms
 will be reported.
- Number of AEs/SAEs will be presented overall and by treatment arm.
- Number of patients experiencing a specific number of AEs/SAEs, overall and by treatment arm.
- Distribution of (S)AEs by grade and CTCAE category, separately for the two treatment arms. Six columns, one for each grade and one for all (any) grades, will be shown (for each arm). An additional column (by arm) indicating which events were also SAEs will be also available. In this column, the frequency of the SAEs and the severity grade will be given. The percentages that will accompany the frequencies will be based on the respective frequency of an event over the total number of patients in the safety cohort and specific treatment arm. This table will include all (S)AEs irrespective of their relation to the trial treatment.
- Analogous table focusing only on the treatment related (S)AEs.
- Number and corresponding percentages of treatment related (S)AEs by grade, leading either to treatment discontinuation or death will be summarized for the two treatment arms.

- Maximum severity of adverse events (AE/SAE) for patients, overall and by treatment arm.

- Number of SAEs by center
- Detailed information of pulmonary AEs/SAEs of grade ≥3 will be summarized for the two treatment arms.
- The risk difference between the two treatment arms, along with corresponding 95%
 CIs for specific adverse evets (most frequent i.e. ≥15%, of any grade, or perhaps focus on grade ≥3, irrespective of relation to treatment or treatment-related).

Analogous (more concise) information will be reported for the adverse events during the chemo-radiotherapy phase of all enrolled patients who received at least one dose of chemo-radiotherapy (per-protocol safety cohort).

5 Technical details

Data will be primarily analysed using the SAS software package (version 9.4), while the R statistical software will be also used for specific analysis and plots.

All analysis and reviews will be performed according to the Standard Operating Procedures (SOPs) of FSFH statistical team for the final analysis. A second statistician, the reviewing statistician, will independently reproduce all analysis and summary statistics. The reviewing statistician will have an overview of the entire analysis and will explicitly check the code producing tables and figures, as well as any other pieces of code as desired.

Data retrieval information

The final analysis will be based on the database download, that will take place, as soon as the total number of 81 PFS events required according to the statistical design of the trial are observed. Using this database extraction, a set of queries will be produced and forwarded to trial's data manager with the expectation to be answered in a pre-specified time period (approximately four weeks). Corrections and responses based on these queries, will be used for correcting the previously downloaded database, in order to create the final clean dataset to be used for the analysis.

Missing data

- Baseline characteristics

For categorical baseline characteristics if missing cases exist, a separate category named "Missing" will be created. As far as continuous values, missing cases will not be replaced by any statistics calculated over non-missing data.

- Dates:

If the day of the month is missing for any date used in the analysis, the 15th of the month will be used to replace the missing date unless the calculation results in a negative time duration (eg, date of onset cannot be prior to day one date). In this case, the date resulting in one day of duration will be used. If the day of the month and the month are missing for any date used in a calculation, i.e., January 1 will be used to replace the missing date. Missing dates for adverse events will be imputed based on the similar principle.

- Incomplete tumour assessment information

In patients who have no on-study assessments:

 If death is recorded prior to the first planned tumour assessment, the death date will be considered as the date of the PFS event.

- If clinical progression is recorded prior to the first planned tumour assessment, the date of the reported clinical progression will be considered as the date of the PFS event.
- o In all other cases, the patient will be censored at the date of randomization plus 1 day.

Reporting conventions

Regarding the estimates presented in the report, the following rules will be adopted:

- P-values ≥0.001 will be reported with three decimal places
- P-values >0.010 will be reported with two significant demical digits
- P-values less than 0.001 will be reported as "<0.001"
- Means, medians, 95% confidence limits (Cis), quantiles, and any other summary statistics, will be reported with one decimal digit
- Hazard ratios (HRs) and their 95% CI's will be reported to two decimals
- Estimated parameters, not on the same scale as raw observations (e.g. regression coefficients) will be reported to three significant figures.

Multiple recordings of an event for the same patient

There are some cases where a patient may experience the same event (AE/SAE) more than once. In such cases, the event will be counted only once for the calculation of the total number of events reported for the overall safety cohort.

Presentation of results

The results will be presented through tables and figures. A summary of the results will also accompany the main report. First, a short synopsis of the results will be presented through bullets, where only the most important findings will be shown. Following that, a more detailed description of the results will be provided, sectioned in the following order:

- Patient accrual and baseline characteristics
- Follow-up and Treatment administration

- Efficacy analysis
- Safety analysis

All tables and figures will be included in an appendix.
